4.1.3 Selection of doses in the trial

The doses of DE selected for this trial are the same as those used in RE-LY, the Phase III trial for SPAF. In RE-LY, a dose of DE 110 mg b.i.d. was shown to be comparable to warfarin (INR level 2.0–3.0) for preventing strokes and SE, and superior when considering major bleeding risk with a relative risk reduction of 20% ([U09-3249-02](#)). Moreover, there was an approximately 60% reduction in intracranial hemorrhage with both dosages of DE.

The overarching goal related to this exposure level is to achieve superiority in efficacy over ASA with no clinically meaningful excess in bleeding with DE. To achieve this, the dosing instructions applied in this trial are intended to provide homogeneous exposure distribution among patients included into this trial. This means that patients at higher risk of bleeding (i.e. patients aged 75 years or older, or with moderate renal impairment) will receive the lower dose of 110 mg b.i.d. and will achieve an exposure comparable to those patients without these risk factors.

The average exposure across all patients (dabigatran trough levels) will range between the trough levels achieved with 110 mg b.i.d. (median of 66 ng/ml) in the RE-LY trial and the level obtained with 150 mg b.i.d. in RE-LY (median of 93 ng/ml): By utilizing the PK experience from RE-LY ([U09-3249-02](#)) and by considering patients characteristics such as age and renal function from a secondary stroke population included in the PROFESS study ([U08-3667-01](#)), PK modeling has shown that the dosing algorithm in this study will result in a median of plasma trough levels of approximately 77 ng/mL. This exposure is expected to provide superior efficacy over the antiplatelet agent ASA with a comparable low rate of intracranial hemorrhage and the overall ability to deliver an optimal balance of efficacy and safety across the population in the trial.

To obtain the targeted exposure, dabigatran dosing will be adjusted for age and renal function, as follows: Patients will be assigned to DE dose of 150 mg b.i.d., unless they are 75 years or older, or have a CrCl of ≥ 30 to < 50 ml/min, in which case they will receive DE 110 mg b.i.d.

Patients assigned to DE, who initially qualify to receive 150 mg b.i.d., will be down-titrated to 110 mg b.i.d. if their CrCl deteriorates to ≥ 30 - < 50 mL/min, if they experience a GI bleed, or the patient becomes 75 years old during the course of the trial. The patient will be

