asked to return their 150 mg medication and receive 110 mg at an unscheduled visit as soon as possible if their titration is due to drop in CrCl or GI bleed. Patients who turn 75 years old during the trial will receive the 110 mg dose at their next scheduled visit. Patients will only have the option to change the dose once, i.e. there will be no up-titration from 110 to 150 mg b.i.d. if renal function recovers.

Using the characteristics of higher risk populations, modeling shows comparable exposure (median trough concentration of 89 ng/ml) in patients receiving DE 110 mg b.i.d. compared to patients without these risk factors receiving DE 150 mg b.i.d. (median trough concentration of 74 ng/ml) in this trial. Therefore it is concluded that dose adjustment to DE 110 mg b.i.d. may optimize the risk-benefit profile in patients at higher risk of bleeding.

The 100 mg dose of ASA was selected based upon recommendations in current guidelines and because this dosage is widely available and acceptable to most clinicians around the world. Patients assigned to ASA will not change their ASA dose during the course of the trial.

Because assignment of ASA vs. DE is blinded, all patients will have their DE down-titrated via IRT under the age, GI bleed or renal function conditions mentioned above. It will be unknown if the DE kits are active or placebo.

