Some interventions in individual patients may be affected by the characteristics of ASA, others by DE. As study medication is blinded, the Investigator is asked to consider the type of intervention and individual bleeding risk of the patient and to weigh the risk of bleeding against the risk of thromboembolism associated with treatment interruption of assigned study drug. The impact of IRT-assigned optional ASA-co-medication should also be considered. Serum creatinine should normally be checked 1-2 weeks before surgery and the CrCl should be calculated using the Cockcroft-Gault formula ([Section 5.2.3](#)) and the impact on cessation of dabigatran must be considered in patients with reduced renal function.

Where the Investigator becomes aware of a planned procedure/surgery, it is recommended that the study Investigator contact the treating surgeon. Refer to [Appendix 10.2](#) on transitioning to non-study medication in case bridging therapy is chosen.

Study drug assignment should not routinely be unblinded in preparation for an elective procedure. Guidelines for stopping DE in advance of surgery are provided in [Table 4.2.1: 1](#). These guidelines should in general be followed for all patients irrespective of their assigned study medication, unless the situation requires that the antiplatelet effect of ASA be completely resolved. In that case, study drug should be stopped for approximately 7 days or longer depending on the type of intervention planned.

The following is a guide to the discontinuation of study medication before surgery taking renal function and additional risk factors into account. With elective procedures, timing of study medication stop and restart may depend on patient characteristics, type of intervention and type of study medication. Unless explicitly mentioned, the recommendations given for DE can also be applied to patients receiving ASA in the trial.

Table 4.2.1: 1 Recommendations on cessation of blinded study drug in relation to the timing of surgery – under special consideration of the pharmacokinetics of dabigatran

Renal function (CrCl, mL/min) ¹	Estimated half-life in hours (for dabigatran)	Stop study drug before surgery ³	
		High risk of bleeding ²	Standard risk
>80	~13	2 days before	24 h before (2 doses)
≥50-80	~15 (12-18)	2-3 days before	1-2 days before
≥30 to <50	~18 (18-24)	4 days	at least 2 days (> 48 hours)
<30	~27 (>24)	> 5 days	2-5 days

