¹ CrCl can be estimated using serum creatinine by the Cockcroft-Gault formula (see [Section 5.2.3](#)). Patients who develop CrCl <30mL/min during the course of the trial should have study medication temporarily stopped (see [Section 3.3.4.1](#)). For rules and prerequisites to restart DE treatment see [Section 4.2.1](#).

² In addition to renal function, high risk determinants of bleeding risk include type of surgery, advancing age, comorbidities (e.g. major cardiac, respiratory or liver disease), and concomitant use of antiplatelet therapy. The type of surgery associated with a high risk of bleeding includes but is not limited to cardiac surgery, neurosurgery, abdominal surgery or those involving a major organ. Other procedures such as spinal anesthesia may also require complete hemostatic function.

³ If the clinical situation requires that the antiplatelet effect of ASA should be completely resolved, study drug should be stopped for approximately 7 days or longer depending on the type of intervention planned.

During a temporary interruption, thrombosis prophylaxis therapy with commercial antiplatelet(s) or a parenteral anticoagulant e.g. Low-molecular Weight Heparin (LMWH) or Unfractionated Heparin (UFH) (according to local practice) is at the discretion of the Investigator depending on duration of interruption, type of intervention and individual thromboembolic risk of the patient. See [Appendix 10.2](#) for additional information related to initiation of thrombosis prophylaxis and switching back to study medication.

Emergency Procedures

In the case of emergency surgery, study medication should be discontinued (including IRT-assigned optional ASA-co-medication). If possible, surgery should be postponed until 12 hours after the last oral intake of study drug.

In an emergency event, a measure of anticoagulation may become necessary to manage the situation. A physician may consider using the TT, dTT, aPTT or the ECT. Coagulation times should be interpreted in relation to the timing of last drug intake of DE. In RE-LY, patients receiving chronic therapy with dabigatran 150 mg bid, the median peak aPTT was approximately two-fold that of control. Twelve hours after the last dose (trough level), the median aPTT is approximately 1.5-fold that of control, with less than 10% of patients exhibiting two-fold increases in aPTT ([P10-03790](#)).

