An elevated TT or dTT should lead the clinician to consider delaying surgery. If the TT/dTT test is not available, an aPTT, though less precise than the TT, can be used. A persistently prolonged TT or dTT in the absence of heparin, fibrin/fibrinogen degradation products (e.g. with disseminated coagulation activation, sepsis, severe inflammation, and other conditions)

or high concentrations of serum proteins (e.g. myeloma) suggests persistently elevated levels of dabigatran in the blood.

If the condition is considered life threatening, consider reversal of anticoagulation as described under major bleeds. See [Section 4.2.1](#)- Overdose, for more information regarding the specific reversal agent for dabigatran.

Refer also to [Section 4.1.5.2](#) for Emergency Unblinding Procedures.

ASA characteristics relevant in the context of surgery/intervention

The antiplatelet effect of ASA is present up to 7-10 days after medication cessation. Nonetheless, most interventions can be performed without an interruption of ASA therapy. The type of surgery associated with a high risk of bleeding and which may preferably be performed after the antiplatelet effect of ASA has elapsed, includes but is not limited to cardiac surgery, neurosurgery, abdominal surgery or those involving a major organ. Other procedures such as spinal anesthesia may also require complete hemostatic function. It is at the discretion of the Investigator whether a complete resolution of the antiplatelet effect of ASA for a certain procedure is required. In this case, study medication (including IRT-assigned optional ASA-co-medication) may have to be stopped for 7-10 days before the intervention and the risk of thromboembolism during this period must be weighed against the risk of bleeding. ASA does not lead to a prolongation of coagulation times such as aPTT, dTT, TT or ECT.

Dabigatran etexilate characteristics relevant in the context of surgery/intervention

Physicians may consider the following information regarding DE when patients need to undergo surgery or elective procedures. Providing the patient has normal renal function, the onset of effect of dabigatran is within 1 hour of dosing and dabigatran has peak concentrations 2-3 hours after an oral dose. Steady state is reached within 2-3 days.

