Plasma levels of dabigatran in steady state will vary across the population and are particularly affected by renal function. Patients with renal dysfunction may have elevated concentrations of dabigatran due to longer half-lives of active drug (see [Table 4.2.1: 1](#)). Serum creatinine should normally be checked 1-2 weeks before an elective surgery and the CrCl should be calculated using the Cockcroft-Gault formula ([Section 5.2.3](#)). Patients with a CrCl <30mL/min during the course of this study should not be receiving study medication ([Section 3.3.4.1](#)). In patients where renal function is impaired or procedures undertaken which may temporarily compromise renal function, the impact on plasma levels of dabigatran must be considered.

The current version of the IB should be referenced for further information about DE ([U98-3208](#)).

Post Procedural Period

Study medication will be initiated as soon as the patient is hemodynamically stable and hemostasis is achieved. If bridging medication has been used, please see [Appendix 10.2.1](#) on how to switch back to study medication after temporary interruption.

Spinal Anesthesia/Epidural Anesthesia/Lumbar Puncture

Procedures such as spinal anesthesia may require complete hemostatic function. See [Table 4.2.1: 1](#) for recommendations on when to stop DE before spinal/epidural anesthesia.

It is at the discretion of the Investigator whether a complete resolution of the antiplatelet effect of ASA is required for these types of procedures. Complete resolution of ASA antiplatelet effect would require a stop of study medication approximately 7-10 days.

The risk of spinal or epidural hematoma may be increased in cases of traumatic or repeated puncture and by the prolonged use of epidural catheters. After removal of a catheter, resume treatment with study medication after complete hemostasis is achieved, but at minimum an interval of at least 1 hour should elapse for all patients. These patients require frequent observation for neurological signs and symptoms of spinal or epidural hematoma.

[figure not shown]
Major Bleeds

If a patient experiences a major bleed, the study medication should be stopped and the source of bleeding investigated and treated. In an emergency bleeding situation, this may involve coagulation testing (aPTT, TT, dTT, ECT, platelet count as described above in Emergency Procedures), and possibly transfusion, diagnostic procedures and/or surgical hemostasis.

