When Coronary Artery Bypass Grafting (CABG) Surgery is clinically indicated, it should be delayed if possible until at least 12 hours after the last dose of study medication. Elective CABG surgery should be delayed if possible until at least two to three days after the last dose of DE, depending on the renal function of the patient (see [Table 4.2.1: 1](#)). Patients with renal dysfunction may have elevated concentrations of dabigatran due to longer half-lives of active drug (see [Table 4.2.1: 1](#)). If bypass surgery is to start during elevated plasma concentrations of DE there is an increased risk of bleeding. When preparing the patient for cardiopulmonary bypass, this should be taken into account. The procedure may be performed as usual, including the control of the anticoagulation levels using e.g. aPTT, ACT or TT measurements. For further advice on when to stop study medication before surgery see [Table 4.2.1: 1](#).

Overdose

Overdose may require discontinuation of study medication.

As study medication is blinded, the following characteristics of both DE and ASA should also be taken into consideration for the management of overdose:

Overdose with DE

Overdose following administration of DE may lead to hemorrhagic complications due to its PD properties. Suspected overdose with no clinical symptoms requires frequent observation for signs and symptoms of hematoma or overt bleeding. Symptomatic treatment includes the administration of fresh frozen plasma or fresh whole blood. In case of excessive bleeding, special measures to terminate bleeding (concentrates of coagulation factors II, VII, IX or X, or recombinant factor VII) may be indicated, although there is limited clinical data available to support the application of coagulation factors. Consideration should also be given to

administration of platelet concentrates in cases where thrombocytopenia is present. All symptomatic treatment has to be given according to the Investigator's judgment.

For a summary how to manage bleeding on DE see [Figure 4.2.1: 1](#).

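### The elective-CABG stop interval of two to three days omits the 4 days that Table 4.2.1: 1 gives at CrCl 30 to <50 mL/min

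*Protocol*

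**What the plan says.** The paragraph on bypass surgery is in Protocol section 4.2.1, under Interventional / Surgical Management of ACS or stable CAD. It wants elective CABG "delayed if possible until at least two to three days after the last dose of DE, depending on the renal function of the patient", with a reference to Table 4.2.1: 1. It goes on to warn that renal dysfunction can raise dabigatran concentrations, and that "If bypass surgery is to start during elevated plasma concentrations of DE there is an increased risk of bleeding". It refers to the table again with that first warning and once more at its close.

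Table 4.2.1: 1 stands earlier in the same section, under Elective Procedures. The text above it says: "These guidelines should in general be followed for all patients irrespective of their assigned study medication". It has one column for high bleeding risk and one for standard risk. Footnote 2 settles which applies here: "The type of surgery associated with a high risk of bleeding includes but is not limited to cardiac surgery".

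Protocol section 4.1.3 confirms that patients with CrCl 30 to <50 mL/min are treated. It names them with patients aged 75 or older as the exceptions to the 150 mg dose, "in which case they will receive DE 110 mg b.i.d". Section 3.3.4.1 withholds study drug only when CrCl falls below 30.

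**The concern.** The sentence offers a range, says that the choice within it depends on renal function, and cites a table for it. A reader would expect the range to span the table's entries for patients who may be on drug. It stops one row short. The omitted row is the one with the longest half-life among patients who stay on treatment, so the summary fails where renal function matters most. Elsewhere in section 4.2.1 the protocol says that, where renal function is impaired, "the impact on plasma levels of dabigatran must be considered".

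At stake is the timing of a high-bleeding-risk operation. This is the protocol's only CABG-specific interval for elective surgery, and an investigator may take it from the sentence without opening the table. CABG candidates have coronary disease, which is also the only group that may receive the optional ASA kit (section 4.1.1). Footnote 2 lists concomitant antiplatelet therapy as a further determinant of bleeding risk.

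**Working it through.** **Step 1. Compare the sentence with the table.** The sentence gives at least 2 to 3 days. The inputs below are from Protocol Table 4.2.1: 1, high-bleeding-risk column.

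| CrCl (mL/min) | Half-life (h) | High-risk stop | Within the sentence's 2-3 days? |
|---|---|---|---|
| >80 | ~13 | 2 days | yes |
| 50-80 | ~15 (12-18) | 2-3 days | yes |
| 30 to <50 | ~18 (18-24) | 4 days | no |
| <30 | ~27 (>24) | >5 days | no, but study drug is withheld |

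The stated range comes out of the first two rows only. Over the CrCl range in which drug is given (30 and above), the column runs from 2 to 4 days. The standard-risk column does give at least 2 days at CrCl 30 to <50, but footnote 2 places cardiac surgery in the high-risk column.

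**Step 2. Size of the gap at CrCl 30 to <50.** Against the upper end of the sentence: 4 − 3 = 1 day. Against the lower end: 4 − 2 = 2 days. Since the range scales with renal function, the upper end is the likelier choice for this stratum. That is an inference; no text assigns 3 days to it.

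**Step 3. Drug remaining.** Assume a single-exponential decline, so the fraction remaining is 0.5^(hours / half-life), with the table's half-lives.

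- CrCl 30 to <50, 3 days (72 h): 0.5^(72/18) = 6.3%; 0.5^(72/24) = 12.5%.
- CrCl 30 to <50, 4 days (96 h): 0.5^(96/18) = 2.5%; 0.5^(96/24) = 6.3%.
- CrCl 50-80, 2 days (48 h), lower end of the table's own entry: 0.5^(48/15) = 10.9%; 0.5^(48/18) = 15.7%.
- CrCl >80, 2 days (48 h): 0.5^(48/13) = 7.7%.

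**Step 4. The same in concentration.** Section 4.1.3 predicts "comparable exposure (median trough concentration of 89 ng/ml) in patients receiving DE 110 mg b.i.d", and a median trough of 74 ng/mL on 150 mg b.i.d. Take each trough as the level 12 h after the last dose, so that 12 h are subtracted from the elapsed time.

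- CrCl 30 to <50, 3 days: 89 × 0.5^(60/18) = 8.8; 89 × 0.5^(60/24) = 15.7 ng/mL.
- CrCl 30 to <50, 4 days: 89 × 0.5^(84/18) = 3.5; 89 × 0.5^(84/24) = 7.9 ng/mL.
- CrCl 50-80, 2 days: 74 × 0.5^(36/15) = 14.0; 74 × 0.5^(36/18) = 18.5 ng/mL.
- CrCl >80, 2 days: 74 × 0.5^(36/13) = 10.9 ng/mL.

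**Step 5. Compare like with like.** At the central half-lives, 3 days at CrCl 30 to <50 leaves 6.3% (8.8 ng/mL) against 10.9% (14.0 ng/mL) for the permitted 2-day stop at CrCl 50-80. At the longest half-lives it is 12.5% (15.7 ng/mL) against 15.7% (18.5 ng/mL). So 3 days leaves more drug than the table intends for this stratum, but no more than the same column accepts in the next one.

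**The case against.** The strongest reply is that nothing is contradicted. The sentence sets a floor, softened by the qualifier that delay should happen if possible, so a 4-day stop obeys both places. The paragraph gives no CrCl cut-offs, so its dependence on renal function cannot be applied without the table, and it points there three times. This stands, and it rules out reading the two places as conflicting instructions. It does not make the stated range right: a floor said to follow renal function from a cited table should reach that table's value for every treated stratum.

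A second reply is that the dabigatran interval may not decide the matter. Treatment is blinded, and section 4.2.1 names cardiac surgery among the procedures for which it may be preferable to let the ASA effect pass. Study medication then "may have to be stopped for 7-10 days before the intervention". Where the investigator chooses that, the gap disappears. The choice is discretionary, so some cases remain.

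A reader might also infer that patients at CrCl 30 to <50 would go to surgery with an unsafe drug level. The documents do not support that. By the working above, the residual at 3 days is within what the high-risk column tolerates at CrCl 50-80. The paragraph also provides for control of anticoagulation by aPTT, ACT or TT around bypass.

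**Conclusion.** The point holds as a minor internal inconsistency in recommended safety guidance. The sentence's range is wrong as a summary of the table it cites. It is 1 day short at its upper end, in the CrCl 30 to <50 stratum only and for elective CABG only. The documents give no count of such operations; few are to be expected.

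The mismatch itself rests on no assumption beyond footnote 2's placing of cardiac surgery in the high-risk column. The residual-drug figures do rest on assumptions: single-exponential decline, a trough 12 h after the last dose, and medians that cover everyone on 110 mg (age 75 or older as well as reduced CrCl) or on 150 mg. The comparison with CrCl 50-80 uses the 2-day end of that row's 2-3 days.

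It would be wrong to infer any consequence for the trial's results. No endpoint, covariate, analysis set or sample-size input uses this interval.

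**What to change.** Replace the sentence with wording such as: *Elective CABG should, if possible, wait at least two to four days from the last dose of study medication, according to the high-bleeding-risk column of Table 4.2.1: 1 (at least 4 days if CrCl is 30 to <50 mL/min), or longer if the antiplatelet effect of ASA has to be fully resolved.*

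Keep the at-least qualifier, so that the interval remains a minimum. Referring to study medication instead of DE fits the blind and the table's title. The cost is one sentence in an amendment or a short clarification to sites. Data collection, sample size and analysis do not change.

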4.2.2 Restrictions

4.2.2.1 Restrictions regarding concomitant treatment

Corticosteroids, non-steroidal anti-inflammatory drugs (NSAIDs) or anti-rheumatic agents in general should only be used if clinically indicated and benefits are expected to outweigh risks. These medications may increase the risk of gastrointestinal ulcers and gastrointestinal bleeding.

The patients should be advised not to use over-the-counter medications containing additional ASA. In case of the need for pain relief, the use of acetaminophen, diclofenac or ibuprofen instead of ASA should be considered where appropriate. The use of these medications should be limited to the absolute minimum possible time period.

Patients with known need for long-term dual antiplatelet therapy at Visit 1 are excluded from the trial (see [Section 3.3.3](#), exclusion criteria).

The following medications should not be taken concomitantly with study drug:

- ASA (commercial drug /over the counter medications) is not allowed except in the case of CAD where it can be taken if dispensed through IRT as outlined in [Section 4.1.6](#). The use of IRT-assigned ASA should be limited to the absolute minimum possible time period and only if clinically indicated.
- Clopidogrel, ticlopidine, ticagrelor, dipyridamole, dipyridamole+ASA, or prasugrel, and any type of dual antiplatelet therapy
- Vitamin K antagonists (e.g. warfarin, phenprocoumon, acenocoumarol), direct thrombin inhibitors, Factor Xa inhibitors (e.g. rivaroxaban, apixaban, and edoxaban), or other oral anticoagulants
- Fondaparinux, bivalirudin
- Treatment with systemic ketoconazole, itraconazole, posaconazole, cyclosporine, tacrolimus, or dronedarone.
- Concomitant administration of the P-gp inducers rifampicin, St. John`s wort (*Hypericum perforatum*), carbamazepine, or phenytoin, which result in decreased dabigatran plasma concentrations.
- Treatment with parenteral anticoagulants including but not limited to any heparins (UFH or LMWH), and heparinoids (e.g. danaparoid), with the following exceptions:
 - Heparins or other alternate approved parenteral therapy for initial treatment of suspected VTE or ACS if maximum duration is not exceeding 72 hours (see [Section 4.2.1](#)).
- Methotrexate ≥ 15 mg/week

The following medications should not be taken concomitantly with study drug except in clinical scenarios described within [Section 4.2.1](#):

- Fibrinolytic agents (see Section 4.2.1. for exception)
- GPIIb/IIIa antagonists (e.g. abciximab, tirofiban) (see Section 4.2.1 for exception).

The following medications may potentiate or attenuate the effect of the study medication and may only be used, if expressly instructed by a physician to treat an underlying concomitant disease:

- antidiabetics (e.g. sulphonylurea agents)
- digoxin
- methotrexate < 15 mg/week
- valproic acid

- aldosterone antagonists (spironolactone and canrenoate)
- loop diuretics (e.g. furosemide)
- ACE inhibitors
- uricosuric agents (e.g. probenecid, sulphinpyrazone)
- selective serotonin re-uptake inhibitors (SSRI) or selective serotonin norepinephrine re-uptake inhibitors (SNRIs)

Please see [Appendix 10.2.2](#) for guidance on thrombosis prophylaxis or temporary requirement for a parenteral anticoagulant, which requires a temporary stop of study medication.

Bleeding risk may be increased in patients concomitantly treated with selective serotonin re-uptake inhibitors (SSRI) ([U11-1642-01](#)) or selective serotonin norepinephrine re-uptake inhibitors (SNRIs) ([U12-1072-01](#)).

Co-administration of oral anti-platelet (including ASA) and NSAID therapies increase the risk of bleeding ([U09-3249-02](#)). Specifically, with concomitant intake of antiplatelets or strong P-gp inhibitors in patients aged ≥ 75 years, the risk of major bleeding, including gastrointestinal bleeding, increases.

In patients ≥ 75 years, or with previous gastritis, history of peptic ulcer disease or previous gastrointestinal bleeding, the Investigator should consider prescribing a proton-pump-inhibitor (PPI) based on the local prescribing information while receiving NSAIDs/ASA.

A list of common P-gp inhibitors and P-gp inducers, which may affect plasma concentrations of dabigatran, will be provided in the ISF.

If bleeding is clinically suspected, appropriate measures such as testing for occult blood in stool, or testing for a drop in hemoglobin is suggested ([U12-1072-01](#)). Investigators should assess the benefit-risk of the concomitant use of drugs that can promote bleeding, e.g., NSAIDs, or corticosteroids and use them only when the benefits are thought to outweigh the risks.

Development of an Indication for Anticoagulant Therapy During Follow-Up

If a non-AF indication for anticoagulation is identified during the course of the trial (e.g. venous thromboembolism), trial-assigned therapy will be discontinued, and the patients will be switched to an appropriate anticoagulant, which will be determined and followed by the patient's local physician. See [Appendix 10.2.3](#) on how to transition from study drug to a non-study antithrombotic treatment. These patients should continue to attend regularly scheduled visits.

If AF is identified during follow-up and the duration of AF exceeds 6 minutes (either as single episode or cumulative time of several episodes within 20 hours), trial treatment must be discontinued (but the treatment assignment blind should not be broken), and the patient should be switched to standard of care treatment for stroke prevention in atrial fibrillation

(SPAF) (e.g. DE or other) according to local label recommendations. Shorter durations of AF may result in discontinuation of assigned treatment at the Investigator's discretion. These patients should continue to attend regularly scheduled visits.

